## 5 Protocol Deviations

Major protocol deviations, such as significant non-compliance or other serious unforeseen deviations deemed to invalidate the data and affect the conclusions of the trial, will lead to exclusion of data from the PP analysis set. Data will not be excluded from the PP analysis set in case of minor protocol deviations. The list of major protocol deviations include, but is not restricted to:

- Unblinding of assessor
- Treatment not in accordance with randomisation
- Non-compliance with IMP for two or more days
- Administration of hCG for triggering of final follicular maturation was not given despite the triggering criterion for hCG administration was met
- GnRH agonist criterion met but hCG used for triggering of final follicular maturation
- GnRH agonist criterion not met but GnRH agonist used for triggering of final follicular maturation
- Non-compliance with the number of embryos transferred

The rating of protocol deviations in 'minor' and 'major' will be decided by the Ferring clinical team on the basis of a blinded review of data before declaration of clean file and lock of database. If the blinded review identifies serious unforeseen deviations deemed to impact the primary endpoint and affect the conclusions of the trial these will also be rated as major deviations.

The list of major protocol deviations will be detailed and documented in the clean file document prior to database release. Major protocol deviations will be tabulated and listed by subject for all randomised subjects.

## 6 Analysis Sets

### 6.1 Intention-to-Treat Analysis Set

The intention-to-treat (ITT) analysis set is defined as all randomised subjects. Subjects will be analysed according to randomised (planned) treatment.

### 6.2 Full Analysis Set

The FAS is defined as all randomised and exposed subjects. Subjects will be analysed according to randomised (planned) treatment.

### 6.3 Per Protocol Analysis Set

The PP analysis set is defined as all randomised and exposed subjects except those excluded as a result of major protocol deviations as described in Section 5.

## 6.4 Safety Analysis Set

The safety analysis set is defined as all randomised and exposed subjects. Subjects will be analysed according to actual treatment received.

## 6.5 Subgroups

Data will in some cases be reported using the following subgroups:

- Subjects grouped according to AMH at screening ( $<15$  pmol/L,  $\geq 15$  pmol/L)
- Subjects with at least 1 oocyte retrieved
- Subjects with transfer
- Subjects grouped according to number of embryos transferred (single, double)
- Subjects grouped according to ongoing pregnancy type (single, twin, triplet)
- Subjects grouped according to insemination method
- Subjects grouped according to primary reason for infertility
- Subjects grouped according to primary infertility
- Subjects grouped according to smoking status

## 7 Trial Population

All relevant baseline data will be summarised by treatment group (FE 999049, GONAL-F, Total) and age stratum (All age strata,  $<35$ , 35-37, 38-40 years) for both the FAS and the PP analysis sets. Separate tables will be produced by country. The purpose of these tabulations is to characterise the treatment groups and assess the degree of similarity achieved by the randomisation. Baseline data will not be compared using statistical tests. Continuous variables will be presented with number of subjects, mean, standard deviation, median, inter-quartile range, minimum, and maximum. Categorical variables will be presented with number and percentage of subjects within each specific category.

Listings will be produced for the ITT analysis set.

### 7.1 Demographics and Other Baseline Characteristics

#### 7.1.1 Demographics

Demographics and other baseline characteristics (smoking and alcohol habits, body measurements, ultrasound parameters, vital signs, and endocrine parameters) obtained before first exposure to IMP will be listed and presented in summary tables.

#### 7.1.2 Infertility History, Menstrual History and Reproductive History

Infertility history (including previous fertility treatment), menstrual history and reproductive history will be listed and presented in summary tables.

## 7.2 Medical History

All medical history will be coded using MedDRA. The version of MedDRA will be documented. Medical history will be listed and summarised for each medical item. This summary table will be produced overall (i.e. not by age stratum) and by country for the FAS.

## 7.3 Prior and Concomitant Medication

Concomitant medications will be coded using the World Health Organization (WHO) Drug Reference List. Prior and concomitant medication will be summarised by ATC classification 1st level (alphabetically) and ATC classification 2nd level (in decreasing order of frequency). These medications will be tabulated separately for:

- Prior medication, i.e. medication taken exclusively prior to treatment (i.e. with stop date/time before date/time of 1st IMP administration)
- Concomitant medication, i.e. medication taken during the treatment period (i.e. medication that was not stopped before date/time of 1st IMP administration and not started after the end-of-trial visit)

These tables will be produced overall (i.e. not by age stratum) and by country for the FAS.

If the timing of the dose of a medication cannot be established in relation to the administration of IMP, it will be considered as concomitant medication.

Medications will be listed.

## 7.4 Physical Examination and Gynaecological Examination

Physical examination and gynaecological examination performed during screening will be summarised per category. These tables will be produced overall (i.e. not by age stratum) and by country for the FAS.

# 8 Exposure and Treatment Compliance

## 8.1 Extent of Exposure

Duration of treatment (days) is defined as the number of days from first exposure to the day of last exposure (both inclusive). If a subject misses an intermediate dose she will still be considered as being under treatment.

Exposure will be summarised by treatment group (FE 999049, GONAL-F, Total) and age stratum (All age strata, <35, 35-37, 38-40 years) for the safety analysis set. Separate tables will be produced by country. Treatment comparisons will be produced for the overall Pan-Asian trial population and for the Chinese population.

## **Total Gonadotropin Dose and Number of Stimulation Days**

Exposure to gonadotropins will be summarised as the total gonadotropin dose and the number of stimulation days. The total dose will be reported in  $\mu\text{g}$  for FE 999049 and both in IU and  $\mu\text{g}$  for GONAL-F. For subjects in the FE 999049 group the dose on stimulation day 1 will be summarised. The total gonadotropin dose and the number of stimulation days will be compared between treatments using van Elteren test stratified for age and within each age stratum using the Wilcoxon's test.

## **Gonadotropin Dose Adjustments**

Investigator-requested decreases and increases of the gonadotropin dose will be captured during the stimulation period. The requested dose change (decrease / increase / no change) on stimulation day 6 will be tabulated. Further, the number of dose increase requests and number of dose decrease requests per subject will be tabulated. The requested dose change on stimulation day 6 will be compared between treatments using chi-square tests overall and within age stratum.

## **GnRH Antagonist**

Exposure to GnRH antagonist will be summarised as the total dose administered (mg) and duration of treatment (days).

## **Triggering with hCG or GnRH agonist**

Triggering criteria met (hCG, GnRH agonist or none) and drug used for triggering (hCG or GnRH agonist) will be summarised.

## **Progesterone**

Exposure to progesterone will be summarised as the total dose administered (mg) and duration of treatment (days).

## **8.2 Treatment Compliance**

Treatment non-compliance will be presented in listings as non-compliance is expected to be limited.

# **9 Efficacy**

## **9.1 General Considerations**

### **Primary and Secondary Endpoints**

The results of the analyses of the primary endpoint (ongoing pregnancy rate) based on the overall Pan-Asian trial population are essential for the non-inferiority claim. The results obtained for the Chinese trial population is considered supportive of the overall conclusion. If the results for the Chinese trial population are markedly different from those obtained based on the overall Pan-Asian trial population the reasons for this difference will be examined. The secondary endpoints positive  $\beta\text{hCG}$  rate, clinical pregnancy rate, vital pregnancy rate, implantation rate and ongoing implantation rate are considered supportive of the primary endpoint. However, non-inferiority does not need to be established for these secondary endpoints.

The remaining secondary endpoints are intended to provide additional characterisation of the safety and efficacy of FE 999049.

### **Analysis and Presentation of Primary and Secondary Endpoints**

Treatment comparisons will be produced for the overall Pan-Asian trial population and for the Chinese population. Summary tables for the primary endpoint and supportive pregnancy endpoints will be prepared by treatment group and age stratum, and by treatment group and AMH group for both the FAS and PP analysis sets. Separate tables will be produced by country. For the remaining secondary endpoints, summary tables will be prepared by treatment group and age stratum for the FAS.

All tabulations will present the treatment groups and include a total column. Continuous variables will be presented with number of subjects, mean, standard deviation, median, inter-quartile range, minimum, and maximum. Categorical variables will be presented with number and percentage of subjects within each specific category.

Visual displays will be produced as appropriate. All primary and secondary efficacy endpoints will be listed for the FAS.

### **Multiplicity**

No adjustments for multiplicity are required since there is only one primary endpoint and non-inferiority has to be established for both the FAS and the PP analysis sets. In addition, the testing for superiority based on the FAS will be made in a sequential manner, only if non-inferiority is established. The evaluation of the subjects recruited in China will be regarded as supportive. Concerning the secondary endpoints no formal adjustment for multiplicity will be utilised.

### **Missing Data**

For the primary endpoint, ongoing pregnancy rate, occurrence of missing data is unlikely but may occur in case the assessment was not done. For this endpoint, a subject's response is considered as 'negative' unless recorded as 'positive'. Missing observations for the supportive secondary endpoints positive  $\beta$ hCG rate, clinical pregnancy rate and vital pregnancy rate will be considered as 'negative' unless recorded as 'positive'. An exception to this is if a later observation confirms that a previous missing observation was in fact positive. For example, if the  $\beta$ hCG test result is missing but clinical pregnancy is recorded as 'positive' then the  $\beta$ hCG test result will be regarded as 'positive'.

For subjects with transfer but missing information on the number of viable fetuses 10-11 weeks after transfer, the number of viable fetuses will be imputed as zero irrespective of why data are not recorded. For subjects with transfer but missing information on the number of gestational sacs 5-6 weeks after transfer, the number of gestational sacs will be imputed as the number of viable fetuses at 10-11 weeks after transfer.

## 9.2 Primary Endpoint

### 9.2.1 Primary Variable Analysis

This trial has one primary endpoint: Ongoing pregnancy rate. Ongoing pregnancy is defined as at least one intrauterine viable fetus 10-11 weeks after transfer.

The primary objective of this trial is to demonstrate non-inferiority of FE 999049 compared with GONAL-F with respect to the primary endpoint in women undergoing controlled ovarian stimulation. The non-inferiority limit for the difference between treatments (FE 999049 versus GONAL-F) is -10.0% (absolute).

The non-inferiority hypothesis to be tested for the primary endpoint is

$$H_0: \pi_{FE} - \pi_{GF} \leq -10.0\% \text{ against the alternative } H_A: \pi_{FE} - \pi_{GF} > -10.0\%,$$

where  $\pi_{FE}$  and  $\pi_{GF}$  denote the ongoing pregnancy rate after treatment with FE 999049 and GONAL-F, respectively. Non-inferiority will be evaluated based on the overall Pan-Asian trial population.

The primary analyses will be adjusted for the stratification factor (age group) by using the Mantel-Haenszel method to combine results across age strata. In brief, this corresponds to deriving a weighted average across age strata where the weight depends on the number of observations in each treatment group in each age stratum.

For the primary endpoint the null hypothesis ( $H_0$ ) will be tested against the alternative ( $H_A$ ) by constructing a two-sided 95% confidence interval for the difference in ongoing pregnancy rates. If the lower-limit of the two-sided 95% confidence interval is greater than the non-inferiority limit (-10.0%) for both the FAS and the PP analysis set, the null hypothesis will be rejected. In that case it will be claimed that FE 999049 is non-inferior to GONAL-F with respect to ongoing pregnancy rate in women undergoing controlled ovarian stimulation.

If the lower-limit of the two-sided 95% confidence interval for the treatment difference based on the FAS not only lies above the non-inferiority limit (-10.0%) but also above zero then there is evidence of superiority in terms of statistical significance at the 5% level. In this case, the p-value from the test for superiority will be reported and it will be claimed that FE 999049 is superior to GONAL-F for the primary endpoint. The result based on the PP analysis set is not essential for the superiority claim but should lead to a comparable result for a robust interpretation.

There is no need for a multiplicity adjustment when switching from non-inferiority to superiority since it is a simple sequential test procedure. This interpretation is in line with the Food and Drug Administration (FDA) draft guidance on “Multiplicity” and EMA’s “Points to consider on switching between superiority and non-inferiority”.

The two-sided 95% confidence intervals will be constructed based on the asymptotic normal distribution as

$$\frac{\sum w_i RD_i}{\sum w_i} \pm 1.96 \sqrt{\frac{\sum w_i^2 SE(RD_i)^2}{(\sum w_i)^2}},$$

where the sums are over the three age strata (i.e.  $i = 1$  to  $3$ ),  $RD_i = \hat{\pi}_{FE,i} - \hat{\pi}_{GF,i}$  is the observed difference in rates (FE 999049 - GONAL-F) within stratum  $i$ ,

$SE(RD_i) = \sqrt{\frac{\hat{\pi}_{FE,i}(1-\hat{\pi}_{FE,i})}{n_{FE,i}} + \frac{\hat{\pi}_{GF,i}(1-\hat{\pi}_{GF,i})}{n_{GF,i}}}$  is the standard error of the observed difference in rates within stratum  $i$ ,

$w_i = \frac{n_{FE,i} n_{GF,i}}{n_{FE,i} + n_{GF,i}}$  is the weight assigned to stratum  $i$ ,

$\hat{\pi}_{FE,i}, \hat{\pi}_{GF,i}$  are the observed rates for each treatment group and stratum, and

$n_{FE,i}, n_{GF,i}$  are the number of observations in each treatment group and stratum.

A supportive evaluation of the subjects recruited in China will be made and it is expected that the findings among the Chinese trial population will be consistent with the overall findings in the trial. If the results based on the Chinese trial population are markedly different from those obtained based on the overall Pan-Asian trial population the reasons for this difference will be examined.

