### **3.2 Planned Number of Trial Sites and Subjects**

It is planned to randomise 1,000 subjects from 15-30 sites in mainland China and other Asian countries and regions. Of the 1,000 subjects it is expected that 740 subjects will be recruited in mainland China (i.e. possessing a Chinese identification card and having native Chinese parents) and the rest from other Asian countries and regions, potentially Taiwan, South Korea and Vietnam. It is estimated that approximately 1,200 subjects should be screened to achieve 1,000 subjects eligible for randomisation.

The assumptions underlying the sample size calculations will be monitored in a blinded manner (see sections 3.3, 9.1 and 9.10), and the number of randomised subjects may be adjusted up to a maximum of approximately 1,144 subjects, corresponding to an observed ongoing pregnancy rate of 50%.

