**Table 9-2 Sample Size by Ongoing Pregnancy Rate for the PP Analysis Set**

Ongoing pregnancy rate (Assumed equal in the two treatment groups)	Assuming 80% power and -10.0% (absolute) non-inferiority margin		Assuming 90% power and -10.0% (absolute) non-inferiority margin	
	Number of subjects		Number of subjects	
	Per group	Total	Per group	Total
	PP*	PP*	PP*	PP*
25%	295	590	395	790
30%	330	660	442	884
32.2%	343	686	459	918
35%	358	716	479	958
40%	377	754	505	1010
45%	389	778	521	1042
50%	393	786	526	1052

\* Assuming 8% major protocol deviations

Based on an assumed ongoing pregnancy rate of 32.2 % observed in the PP population of the ESTHER 1 trial, N=918 subjects are required in the PP population to obtain a power of 90%. Anticipating at most 8% major protocol deviations this results in N=1000 subjects to be randomised. The power is reasonably robust against deviations from the ongoing pregnancy rate assumption of 32.2%: a 35% ongoing pregnancy rate would still result in a 88.9% power, while lower rates will only increase the power (e.g. 30% yields 91.1% power). Recruiting at least 740 subjects in mainland China is expected to secure that consistency can be established between the results from the overall trial population and the mainland Chinese trial population. In addition, to obtain approval in other Asian countries and regions at least 260 subjects are needed. Thus a total sample size of 1,000 subjects will be recruited for this trial.

A sample size re-assessment is planned and will be done without breaking the blind and without inflating the type 1 error of the trial, in line with the current regulatory guidelines (see section 9.10). The expected maximum number of subjects to be randomised would then be approximately 1,144 (572 per treatment group), corresponding to an observed rate of 50%.

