#### **Analysis and Presentation of Primary and Secondary Endpoints**

Summary tables and treatment comparisons for the primary endpoint and supportive secondary endpoints will be presented overall, by age stratum and country for both the FAS and PP analysis sets. Treatment comparisons will be produced for the overall trial population and for the mainland Chinese population. As applicable for the remaining secondary endpoints, summary tables and treatment comparisons may be presented overall and by age stratum for the FAS and PP analysis sets.

All tabulations will present the treatment groups and include a total column. Continuous variables will be presented with number of subjects, mean, standard deviation, median, inter-quartile range, minimum, and maximum. Categorical variables will be presented with number and percentage of subjects within each specific category.

All statistical tests will be performed using a two-sided test at a 5% significance level. Treatment differences will (where appropriate) be presented with 95% confidence intervals and p-values corresponding to the statistical test of the hypothesis of 'equal effect' against the alternative of 'different effect'.

Visual displays will be produced as appropriate. All primary and secondary efficacy endpoints will be listed for the FAS.

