#### 3.2 Determination of Sample Size

The primary objective of this trial is to demonstrate non-inferiority of FE 999049 compared with GONAL-F with respect to ongoing pregnancy rate in women undergoing controlled ovarian stimulation. The non-inferiority limit for the difference between treatments (FE 999049 versus GONAL-F) is -10.0% (absolute) for the primary endpoint.

Since this is a non-inferiority trial, the full analysis set (FAS) and the per-protocol (PP) analyses are equally important, i.e. non-inferiority should be established for both analysis sets in order to have a robust conclusion. Therefore, the expected proportion of subjects with major protocol deviations should be taken into account when setting the total sample size for the trial. The proportion of subjects with major protocol deviations is assumed to be at most 8%.

The trial is designed to have 90% power of achieving the primary objective for the overall Pan-Asian trial population and 80% power in the Chinese population. The number of subjects needed to achieve 90% power depends on the assumptions regarding the ongoing pregnancy rate. Based on an assumed ongoing pregnancy rate of 32.2% observed in the PP population of the ESTHER 1 trial, N=918 subjects are required in the PP population to obtain a power of 90%. Anticipating at most 8% major protocol deviations this results in N=1000 subjects to be randomised. The power is reasonably robust against deviations from the ongoing pregnancy rate assumption of 32.2%: a 35% ongoing pregnancy rate would still result in a 88.9% power, while lower rates will only increase the power (e.g. 30% yields 91.1% power). Recruiting at least 740

subjects in China is expected to secure that consistency can be established between the results from the overall Pan-Asian trial population and the Chinese trial population. In addition, to obtain approval in other Asian countries at least 260 subjects are needed. Thus a total sample size of 1,000 subjects will be recruited for this trial.

A blinded sample size reassessment will take place when data on the primary endpoint are available for 70% of the planned subjects or when 800 subjects are randomised, whichever comes first. The sample size reassessment will be done without breaking the blind and without inflating the type I error of the trial, in line with the current regulatory guidelines for non-inferiority trials by FDA and in general by EMA.

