A restricted recalculation rule for the sample size reassessment will be used. Accordingly 1,000 subjects should be randomised to achieve sufficient power if the ongoing pregnancy rate is 32.2%. If the ongoing pregnancy rate is above the expected 32.2%, the sample size can be adjusted up to a maximum of 1,144 (572 per treatment group), corresponding to an ongoing pregnancy rate of 50%. If the rate is below the expected 32.2% the sample size will not be decreased below the planned 1,000 subjects.

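### The China consistency check sets mainland women against an overall population that is about 74% mainland, so a regional difference shows at about a quarter of its size, and no pooled non-mainland estimate or regional contrast is specified

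*SAP*

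**What the plan says.** Protocol 3.2 states: "Of the 1,000 subjects it is expected that 740 subjects will be recruited in mainland China". The rest come from other Asian countries and regions. SAP 3.2 treats 740 as a minimum and gives the reason: recruiting that many in China "is expected to secure that consistency can be established between the results from the overall Pan-Asian trial population and the Chinese trial population". It continues: "In addition, to obtain approval in other Asian countries at least 260 subjects are needed". Protocol 9.1 says the same.

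The check itself is in SAP 9.2.1 and is repeated in 9.1. The Chinese subjects get a supportive evaluation, and action follows if their results are "markedly different from those obtained based on the overall Pan-Asian trial population the reasons for this difference will be examined". Neither document says how large a gap counts as marked. Protocol 9.7.2 goes one step further than the SAP and would also weigh what such a gap means for the trial's overall conclusion.

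On output, SAP 9.1 says: "Treatment comparisons will be produced for the overall Pan-Asian trial population and for the Chinese population". For the primary endpoint it adds summary tables by arm in the FAS and PP sets, produced separately for each country. Protocol 9.7.1 says: "Summary tables and treatment comparisons for the primary endpoint and supportive secondary endpoints will be presented overall, by age stratum and country". Its next sentence, however, names only the overall and mainland Chinese populations for treatment comparisons. SAP section 12 lists departures from the protocol and does not mention comparisons by country.

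For the primary endpoint, the only planned test of homogeneity is across sites (Protocol 9.7.2, SAP 9.2.2).

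**The concern.** The comparison sets a part against a whole that mostly consists of that part. If the effect in mainland China differs from the effect elsewhere, most of the difference cancels, because the mainland women pull the overall result towards their own. With no threshold, the judgement rests on the visible size of the gap, which is the quantity that the design makes small.

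Recruitment was set partly so that consistency could be assessed, and at least 260 women are recruited elsewhere with approval in those countries in mind. The data for a direct look at regional consistency will exist. The SAP does not specify the estimate that would show it.

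**Working it through.** **Inputs.** 740 mainland and 260 non-mainland of 1,000; 1:1 allocation; ongoing pregnancy rate 32.2% in both arms; margin -10.0 points; two-sided 95% interval; at most 8% lost to the PP set; maximum total 1,144 (Protocol 3.2 and 9.1; SAP 3.1, 3.2 and 9.2.1).

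**The plan's own figures.** Per group, n = 2 × 0.322 × 0.678 × (1.960 + z)² / 0.10².
- 90% power (z = 1.282): 459 per group, 918 in total, as stated. 918 / 0.92 = 998, stated as 1,000.
- 80% power (z = 0.842): 343 per group, 686 in total, as in Protocol Table 9-2.
- Mainland: 740 × 0.92 = 680.8 in the PP set, which gives 79.7% power against the stated 80%.

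The sample size therefore reproduces and is not in question.

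**Dilution.** Let f be the mainland share. Then overall ≈ f × mainland + (1 − f) × other, so

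mainland − overall = (1 − f) × (mainland − other).

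With f = 0.74 the factor is 0.26. If the total rises to 1,144, it lies between 260/1,144 = 0.23 and (1,144 − 740)/1,144 = 0.35, depending on where the extra women come from.

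The SAP's estimator weights by age stratum, so the formula is an approximation. The documents give no age mix or age-specific rates. In a simulation that assumed control rates of 38%, 30% and 20% in the three age strata and a 10-point regional difference, the factor was 0.26. This held with the same age mix in both regions (70/20/10%) and with different mixes (75/15/10% against 50/25/25%).

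**Standard errors at 32.2%, FAS.**
- Mainland: √(2 × 0.322 × 0.678 / 370) = 3.44 points.
- Non-mainland: √(2 × 0.322 × 0.678 / 130) = 5.80 points; 95% half-width 1.96 × 5.80 = 11.4.
- Mainland minus non-mainland: √(3.44² + 5.80²) = 6.74 points; half-width 13.2.
- Mainland minus overall: 0.26 × 6.74 = 1.75 points.

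In the PP set (× 0.92 in numbers) the half-widths are 11.8 for non-mainland and 13.8 for the contrast.

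**What each comparison shows.** Power below is for a direct two-sided 5% test of the contrast in the FAS: Φ(D/6.74 − 1.96) + Φ(−D/6.74 − 1.96).

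| True regional difference D (points) | Gap in mainland versus overall | Power of direct test |
|---|---|---|
| 5 | 1.3 | 12% |
| 10 | 2.6 | 32% |
| 15 | 3.9 | 61% |
| 20 | 5.2 | 84% |

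**Example.** Suppose the observed difference is 0 in mainland China and −15 points elsewhere. Overall it is 0.26 × (−15) = −3.9. Protocol Table 9-1 lets non-inferiority be claimed with an observed deficit of up to 4.0 points, so the claim could succeed. The gap between China and overall is 3.9 points. The pooled non-mainland estimate, which the SAP does not specify, would be −15 with a 95% interval of about −26 to −4.

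**The case against.** Several points on the other side stand.

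- **The noise shrinks with the signal.** For a 10-point regional difference, 2.6/1.75 and 10/6.74 are both 1.48. A formal test would give the same answer on either scale. The dilution misleads only someone who judges the raw gap without its precision. That is nevertheless what the plan invites, since it sets neither a test nor a threshold.
- **The planned comparison is the one the documents name.** Consistency is defined as overall against China, and China has its own treatment comparison with a stated 80% power. No objective asks for a non-mainland effect, and no analysis is tied to the 260 women. This argues for adding to the comparison and against replacing it.
- **The evaluation is supportive**, and the direct contrast is imprecise.

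Three stronger readings are tempting and are not supported.

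- A reader might infer that the non-mainland effect can never be seen. The by-country tables give rates by arm, from which crude differences can be read, and the pooled difference is roughly (overall − 0.74 × China)/0.26. What is missing is a specified pooled estimate with its interval.
- A reader might infer that the plan would declare a discrepant region consistent. There is no rule that declares anything; the documents only promise to examine a marked difference.
- A reader might infer that the SAP silently dropped a firm commitment to comparisons by country. Protocol 9.7.1 is ambiguous, and the SAP follows the second of its two sentences. The table shells are in a separate document that was not available.

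The site-homogeneity test is a partial answer, because sites lie within countries. It is not aimed at region, it spreads over 15 to 30 sites, and the SAP excludes sites with uniform outcomes or with at most one subject in an arm.

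**Conclusion.** The concern holds as a weakness in a supportive analysis. At the planned 740/260 split, the China-versus-overall gap is 0.26 of the mainland-versus-non-mainland difference (0.23 to 0.35 if the total reaches 1,144). With no threshold, a regional difference of 10 to 15 points could readily be judged consistent by eye. The SAP specifies neither a pooled non-mainland difference with an interval nor a regional contrast, and its by-country output for the primary endpoint is arm-level summaries. Protocol 9.7.1, SAP 9.1 and SAP section 12 need to be reconciled on treatment comparisons by country.

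The factor depends on the mainland share; the age-stratified check also rests on the assumed age mixes and rates. The standard errors assume 32.2% in both arms and both regions. The non-inferiority decision, made on the overall population in the FAS and PP sets, is unaffected.

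**What to change.** Keep the China and overall analyses in SAP 9.2.1 and add, for the FAS and PP sets:

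1. the age-stratified Mantel-Haenszel difference with its 95% interval for the pooled non-mainland group;
2. the mainland minus non-mainland contrast with its 95% interval, with variance equal to the sum of the two regional variances.

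Label both supportive and base the consistency discussion on the contrast and its interval alongside the China-versus-overall comparison. Report them as estimates and not as a pass/fail test: with 32% power for a 10-point difference, a non-significant result would say little.

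State in SAP 9.1 whether treatment comparisons by country will be produced. If they will not, record this in section 12 and clear up the two sentences in Protocol 9.7.1.

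The cost is some SAP wording and a further run of the existing primary-analysis program, with no new data. The drawback is wide intervals, which the text should say in advance.
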